# 7. DEFINITIONS OF POPULATIONS

Any protocol deviations, including those due to coronavirus disease 2019 (COVID-19) and related restrictions (see Section 8.1.1), will be considered prior to database lock for their importance and taken into consideration when assigning subjects to populations.

## 7.1. All Subjects Population

The all subjects population will include all subjects who signed the ICF and had any study assessment recorded in the database per the protocol.

# 7.2. Safety Population

The safety population will include all subjects who received at least 1 dose of sotorasib and have at least 1 postdose safety assessment.

# 7.3. Pharmacokinetic Population

The PK population will include all subjects who received at least 1 dose of sotorasib and have evaluable PK data. A subject may be excluded from the PK summary statistics and statistical analysis if the subject has an adverse events of vomiting that occurs at or before 2 times median time to maximum concentration or diarrhea within 24 hours of dosing.

#### 8. STATISTICAL METHODOLOGY

#### 8.1. General

Listings will be provided for all data captured in the database, with the exception of medical history. Listings will include all subjects assigned to the all subjects population and include data up to the point of study completion or discontinuation. Subjects are generally considered to have completed the study if they complete the scheduled end of study visit (rather than early termination visit). Any subject who discontinues the study will be identified accordingly in the listings. Summaries and statistical analyses will include the subjects assigned to the relevant population based on data type.

Data analysis will be performed using the SAS® statistical software package Version 9.4 (or higher if a new version is issued during the study).

Analysis Data Model (ADaM) datasets will be prepared using Clinical Data Interchange Standards Consortium (CDISC) ADaM Version 2.1 (or higher if a new version is issued during the study) and CDISC ADaM Implementation Guide Version 1.1 (or higher if a new version is issued during the study). Pinnacle 21 Enterprise Version 4.2.0 (or higher if a new

**CONFIDENTIAL** 

version is issued during the study) will be utilized to ensure compliance with CDISC standards.

Caution should be used when interpreting results from the statistical analyses conducted in this study because the sample size is not based on power calculations.

Where reference is made to 'valid' data, this refers to non-missing data which meet the predetermined criteria (eg, are not flagged for exclusion).

Where reference is made to 'all calculations', this includes, but is not limited to, summary statistics, statistical analyses, baseline derivation, changes from baseline, percentage changes from baseline, and any parameter derivations.

All figures will be produced on linear-linear or discrete-linear scales, as applicable, unless specifically stated otherwise.

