#### 5. SAMPLE SIZE JUSTIFICATION

The study will require at least 132 subjects completing the study to establish equivalence between the 2 groups with 90% power. This test is based on a 2-sided ratio of means test for a 2 x 2 crossover design for continuous data with significance level 5%. The ratio of means between treatment and control groups under the alternative hypothesis is 0.95. This test assumes lower and upper equivalence limits of 0.8 and 1.25, respectively, and root mean squared error of the log ratio equal to 0.472. Assuming approximately 10% drop out rate, approximately 146 subjects (73 subjects per treatment) will be enrolled in this study.

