# **Bioequivalence:**

A statistical analysis will be conducted to investigate the bioequivalence of 960 mg sotorasib administered orally as 3 x 320 mg tablets (test 1) to 960 mg sotorasib administered orally as 8 x 120 mg tablets (reference treatment) for  $AUC_{last}$ ,  $AUC_{inf}$ , and  $C_{max}$ . Data from the entire study population will be used for this analysis.

The natural log (ln)-transformed PK parameters will be analyzed using a mixed model. The model will include treatment, period, and sequence as fixed effect and subject nested within sequence as a random effect.

For AUClast, AUCinf, and Cmax separately, the least squares mean (LSM) for each treatment, difference in LSMs between the test 1 and reference treatments, and corresponding 90% confidence interval (CI) will be calculated; these values will then be backtransformed to give the geometric least square mean (GLSM), ratio of GLSMs, and corresponding 90% CI.

Additionally, the pooled estimate (across all treatments) of the within-subject CV will be calculated, and residual plots will be produced to assess the adequacy of the model(s) fitted.

It will be concluded that the test treatment is bioequivalent to the reference treatment if, for Cmax and AUCs, the 90% CI for the ratio of GLSMs is completely contained within the predefined interval of (0.8000, 1.2500). This procedure is equivalent to Schuirmann's two one-sided tests at the 0.05 level of significance.

Examples of the SAS code that will be used are as follows:

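### Does the SAP's remark that the sample size was not based on power calculations undermine the powered bioequivalence conclusion?

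*SAP*

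**What the plan says.** SAP Section 8.1 (General) tells the reader to be cautious with results of the study's statistical analyses "because the sample size is not based on power calculations". It does not limit this to any one analysis. Both copies of the SAP in the file carry the sentence.

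SAP Section 5 says otherwise: "The study will require at least 132 subjects completing the study to establish equivalence between the 2 groups with 90% power". It names the design and level ("This test is based on a 2-sided ratio of means test for a 2 x 2 crossover design for continuous data with significance level 5" per cent). The inputs are an assumed true ratio of 0.95, limits of 0.8 to 1.25, and variability given as "root mean squared error of the log ratio equal to 0.472". It then sets enrolment: "Assuming approximately 10% drop out rate, approximately 146 subjects (73 subjects per treatment) will be enrolled in this study". Protocol Section 8.1 gives the same calculation.

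The Bioequivalence part of SAP Section 8.5.3 states the decision rule. Bioequivalence is concluded if the 90% confidence intervals for the geometric mean ratios of Cmax and the AUCs lie wholly within 0.8000 to 1.2500. The SAP equates this with "two one-sided tests at the 0.05 level of significance".

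**The concern.** The two SAP statements cannot both be true of the primary analysis. The caveat sits under a general heading, and SAP Section 8.6.6 plans no inferential safety analysis. The only inferential analyses are therefore the bioequivalence model and the food-effect model, so on its face the caveat covers the primary conclusion.

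A reader could take this in two ways. Either the Section 5 calculation is not a real basis for the 146 subjects, or the SAP is asking for a confirmatory result to be discounted. SAP Section 1 adds some weight, because it says the SAP supersedes the protocol's statistical considerations. If either reading held, the study's single main answer would be in doubt. At the least, an incorrect caveat could be copied into the study report.

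**Working it through.** **Step 1. Is Section 5 a real power calculation?**

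Inputs, all from SAP Section 5 unless noted:
- log-scale within-subject SD s = 0.472
- true ratio 0.95, so ln(0.95) = −0.0513
- limits 0.8 and 1.25, so ±0.2231 on the log scale
- 2 × 2 crossover with 1:1 allocation (Protocol Section 5.6)
- one-sided level 0.05 for each of two tests (decision rule in SAP Section 8.5.3)

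Formulas: standard error of the log ratio SE = s × √(2/N), with N − 2 degrees of freedom. Power is the probability that the whole 90% interval falls inside the limits, integrated over the distribution of the estimated variance.

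At N = 132, SE = 0.472 × √(2/132) = 0.0581. The assumed ratio is 0.1719 from the lower limit and 0.2744 from the upper limit, which is 2.96 and 4.72 standard errors.

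| Completers | Exact power |
|---|---|
| 130 | 0.8976 |
| 132 | 0.9017 |
| 146 | 0.9262 |

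The smallest even N that reaches 90% is 132, the stated figure. The normal approximation agrees closely: 2 × [0.472 × (1.645 + 1.282) / 0.1719]² = 129.2, or 130 as an even number.

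Other readings of the inputs do not give 132. A one-sided level of 0.025 needs 162. Treating 0.472 as the SD of the within-subject difference needs 68. Treating it as a coefficient of variation needs 120. So the Section 5 description of a two-sided 5% test is best read as two one-sided tests at 0.05 each, which matches the decision rule.

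Enrolment: 1 − 132/146 = 9.6%, consistent with the stated dropout of about 10%.

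The sample size does rest on a power calculation. The Section 8.1 sentence is false for the primary comparison.

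**Step 2. What does the sentence control?**

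| Item | Where it is fixed | Depends on the sentence? |
|---|---|---|
| Number enrolled and completing | SAP Section 5; Protocol Section 8.1 | No |
| Model and transformation | SAP Section 8.5.3 | No |
| Error rate, 0.05 per one-sided test | SAP Section 8.5.3 | No |
| Bioequivalence conclusion | SAP Section 8.5.3, stated without condition | No |

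The chance of wrongly declaring bioequivalence is held at 5% by the interval rule, however N was chosen. Once the data are in, the width of the 90% interval shows the precision reached. A remark about the origin of N adds nothing to it.

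**Step 3. Where would the remark be true?**

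It is true of the food-effect comparison, which uses 14 subjects and has no stated power basis. With 13 degrees of freedom the 90% interval is the estimated ratio divided and multiplied by exp(1.771 × s × √(2/14)) = exp(0.669 × s). The documents give no SD for fed against fasted dosing, so s is assumed:

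| Assumed s | Factor |
|---|---|
| 0.30 | 1.22 |
| 0.472 (borrowed from Section 5) | 1.37 |
| 0.60 | 1.49 |

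That is imprecise. However, the Food Effect part of SAP Section 8.5.3 asks only for a ratio and its 90% interval, with no limits and no decision rule, so it is already estimation.

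**The case for a change.** The best case for acting is that the sentence is false, unrestricted, and sits in the document that governs the analysis. Correcting it would cost one line. The later document history in the second SAP copy records other corrections and leaves this one. A false caveat on the primary result could draw avoidable questions, while the comparison that deserves caution is not singled out.

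The factual part stands: the sentence is wrong for the primary analysis, and no other text restricts it. The consequences do not stand. The supersession clause does not help, because the power calculation is in the SAP itself. This is a document disagreeing with itself, not an SAP overriding a protocol. SAP Section 10 declares no significant change from the protocol's analyses, so the power basis has not been withdrawn. Nor does the SAP call the bioequivalence test exploratory; it only advises caution. The sentence is more plausibly template text than an intended rule. Section 6, for example, illustrates treatment sequences with a placebo, and this study has none. That explanation is an inference, but the conclusion does not depend on it.

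**Conclusion.** The contradiction is real but clerical, and no change to the plan is needed. An analyst who follows the SAP as written enrols the same 146 subjects, fits the same model, computes the same 90% intervals and reaches the same bioequivalence decision. The power at 132 completers remains 90.2% under the stated assumptions (ratio 0.95, log-scale SD 0.472, one-sided level 0.05 per test). Removing the sentence would alter no estimate, error rate, bias or safety measure.

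What remains is a small risk that the caveat is repeated in the report. A report author has the full calculation in SAP Section 5 and in the protocol to set against it. For the food effect, the reported interval will itself show how little 14 subjects can establish.

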# 8.1.1. Handling of Data Quality Issues Due to Coronavirus Disease 2019 and Related Restrictions

Due to COVID-19 and related restrictions, there is a high risk for impact to data integrity, with the recognized potential for:

- Missed visits, caused by, for example:
  - Subject unable to travel to site due to restrictions, the need to quarantine, or COVID-19 infection
  - o Subject unwilling to go to site due to fear of COVID-19 infection
  - Site postponing subject's visit due to investigator not being available (eg, if they have been dispatched to hospital handling COVID19 infections)
- Site unable to replenish supply of investigational product
- Incomplete data entry by sites due to limited resources to support study or no access to source documents or to eCRF
- Outstanding source document verification (SDV) due to sponsor or country restrictions on remote SDV, or no or limited access to site(s) for on-site visits
- Unanswered queries

At the time of the reporting of the study results, all protocol deviations due to COVID-19 or related restriction will be assessed for their severity and impact on the analyses. If needed, appropriate statistical methods will be applied as a mitigating action (eg, data might be categorized into 2 analysis groups, with and without COVID-19 and related restrictions impact); however, this will exclude any imputations of the missing values. Any mitigating actions will be agreed with Amgen Inc. in advance and identified in the CSR.

# 8.1.2. Calculation of the Summary Statistics

For continuous data the following rules will be applied:

- Missing values will not be imputed, unless specifically stated otherwise.
- Unrounded data will be used in the calculation of summary statistics.
- If the number of subjects with valid observations (n) <3, summary statistics will not be calculated, with the exception of n, minimum, and maximum.
- In general, as early termination data are not associated with any scheduled timepoint, they will be excluded from all calculations of summary statistics and statistical analyses. Exceptions may be made where justified.

For categorical data the following rules will be applied:

- For ordered categorical data (eg, AE severity), all categories between the possible minimum and maximum categories will be included, even if n = 0 for a given category.
- For non-ordered categorical data (eg, race), only those categories for which there is at least 1 subject represented will be included; unless specifically stated otherwise.
- Missing values will not be imputed, unless specifically stated otherwise. A 'missing' category will be included for any parameter for which information is missing. This will ensure that the population size totals are consistent across different parameters.

# 8.1.3. Triplicate Readings

For 12-lead electrocardiogram (ECG) data only, where triplicate readings are taken, the mean of triplicate readings will replace the separate individual triplicate readings in all calculations.

In case of incomplete triplicate readings (eg, only 2 out of 3 readings were recorded), the mean and/or medians will be calculated, as appropriate, based on the number of readings available.

## 8.1.4. Repeat and Unscheduled Readings

For vital signs and 12-lead ECG data only, any predose value recorded in addition to the original value or a postdose value recorded within 15 minutes of the original value will be defined as a repeat value; any postdose value recorded more than 15 minutes after the original value will be defined as an unscheduled value. For all other data types (eg, laboratory parameters), any value recorded in addition to the original value will be defined as an unscheduled value.

The original value will be replaced by the last associated repeat value in all calculations.

Page 13 of 47

As unscheduled values are not associated with any scheduled timepoint, they will be excluded from all calculations.

# 8.2. Subject Disposition and Population Assignment

Subject disposition and population assignment will be listed.

A summary table by treatment will be provided, based on the safety population.

# 8.3. Screening Demographics and Baseline Characteristics

The screening demographics and baseline characteristics including sex, age, race, ethnicity, height, body weight, and body mass index will be listed.

A summary table by treatment will be provided, based on the safety population.

#### 8.4. Prior and Concomitant Medication

Prior medication will be defined as medication that ends prior to dosing. Concomitant medication will be defined as medication that starts during or after dosing or starts but does not end prior to dosing.

Prior and concomitant medications will be coded using the World Health Organization Drug Dictionary (WHODrug) Global, Format B3, Version September 2020 (or later if a new version is issued during the study; see the data management plan [DMP] for more details). Prior and concomitant medications will be listed.

#### 8.5. Pharmacokinetic Assessments

## 8.5.1. Pharmacokinetic Analysis

The following PK parameters will be determined on Day 1, Day 4, and Day 7, data permitting, from plasma concentrations of sotorasib using noncompartmental methods in a validated installation of Phoenix WinNonlin (Certara, Version 8.1 or higher):

Parameter	Unitsa	Definition
AUC last	h*ng/mL	area under the plasma concentration-time curve from time zero to the last quantifiable concentration b
$\mathrm{AUC}_{\mathrm{inf}}$	h*ng/mL	area under the plasma concentration-time curve from time zero extrapolated to infinity c
$C_{\text{max}}$	ng/mL	maximum observed plasma concentration
$t_{max}$	h	time of the maximum observed plasma concentration
$t_{last}$	h	time of the last quantifiable plasma concentration
$t_{1/2}$	h	apparent terminal elimination half-life
CL/F	L/h	apparent total clearance
V z /F	L	apparent volume of distribution during the terminal phase

<sup>a Units are based on concentration units (provided by the bioanalytical lab or preferred units for presentation of PK parameters) and dose units used in the study.

CONFIDENTIAL

**CONFIDENTIAL** Protocol Reference: 20210093

Additional PK parameters may be determined where appropriate.

Pharmacokinetic analysis will be carried out where possible using actual dose administered (mg) and actual postdose blood sampling times. If an actual time is missing, nominal times may be used with sponsor's approval.

The parameters Cmax, tlast, and tmax will be obtained directly from the concentration-time profiles.

For multiple peaks, the highest postdose concentration will be reported as Cmax. In the case that multiple peaks are of equal magnitude, the earliest tmax will be reported.

# 8.5.1.1. Criteria for the Calculation of Apparent Terminal Elimination Rate Constant and Half-life

The start of the terminal elimination phase for each subject will be defined by visual inspection and generally will be the first point at which there is no systematic deviation from the log-linear decline in concentrations.

The apparent terminal elimination rate constant ( $\lambda_z$ ) will only be calculated when a reliable estimate can be obtained using at least 3 data points, preferably not including Cmax, and the adjusted coefficient for determination of exponential fit ( $\mathbb{R}^2$ -adj) of the regression line is  $\geq 0.8$ . Parameters requiring  $\lambda_z$  for their calculation (eg, AUCinf,  $t_{1/2}$ , CL/F, and  $V_z$ /F) will only be calculated if the  $R^2$ -adj value of the regression line is  $\geq 0.8$ .

The following regression-related diagnostic PK parameters will be determined, when possible:

Parameter	Units	Definition
%AUC extrap	%	percentage of area under the concentration-time curve due to extrapolation from the last quantifiable concentration to infinity
$\lambda_{\mathrm{z}}$	1/h	apparent terminal elimination rate constant
$\lambda_z$ Upper	h	end of exponential fit
$\lambda_z$ Lower	h	start of exponential fit
$\lambda_z \; N$	NA	number of data points included in the log-linear regression
$\lambda_z$ Span Ratio	NA	time period over which $\lambda_z$ was determined as a ratio of $t_{1/2}$
R  -adj	NA	adjusted coefficient for determination of exponential fit

Where possible, the span of time used in the determination of  $\lambda_z$  (ie, the difference between  $\lambda_z$ Upper and  $\lambda_z$  Lower) should be  $\geq 2$  half-lives. If the  $\lambda_z$  Span Ratio is  $\leq 2$ , the robustness of the  $t_{1/2}$  values will be discussed in the CSR.

<sup>b The AUC will be calculated using the linear trapezoidal rule.

<sup>c Based on the last observed quantifiable concentration

# 8.5.1.2. Criteria for Calculation and Reporting of Area Under the Concentration-time Curve

The minimum requirement for the calculation of AUC will be the inclusion of at least 3 consecutive concentrations above the lower limit of quantification (LLOQ). If there are only 3 consecutive concentrations, at least 1 should follow  $C_{max}$ .

If the extrapolated area is >20%, AUCinf (and derived parameters) will be flagged and may be excluded from the summary statistics and statistical analysis at the discretion of the sponsor or pharmacokineticist.

If AUCinf cannot be determined reliably for all subjects and/or treatments, an alternative AUC measure, such as AUC to a fixed timepoint or AUClast, may be used in the statistical analysis upon sponsor approval.

# 8.5.1.3. Criteria for Handling Below the Limit of Quantification or Missing Concentrations for Pharmacokinetic Analysis

Plasma concentrations below the limit of quantification (BLQ) will be assigned a value of 0 before the first measurable concentration and thereafter BLQ concentrations will be treated as missing. The following rules apply to the specific situations defined below:

- If an entire concentration-time profile is BLQ, it will be excluded from PK analysis.
- Where 2 or more consecutive concentrations are BLQ at the end of a profile, the profile will be deemed to have terminated and any further quantifiable concentrations will be set to missing for the calculation of the PK parameters, unless they are considered to be a true characteristic of the profile of the drug.
- If a predose plasma concentration is missing, it will be set to 0 by default within Phoenix WinNonlin.

# 8.5.1.4. Treatment of Outliers in Pharmacokinetic Analysis

If a value is considered to be anomalous due to being inconsistent with the expected PK profile, it may be appropriate to exclude the value from the PK analysis. However, the exclusion of any data must have strong justification and will be documented in the CSR.

Any quantifiable predose concentration value in the first treatment period will be considered anomalous and set to missing for the PK analysis. This will be set to 0 by default in Phoenix WinNonlin.

If the predose concentration is >5% of  $C_{max}$  in the second or third treatment periods, all PK concentration and parameter data will be flagged and reported but excluded from the summary statistics and statistical analysis for that period.

#### 8.5.2. Presentation of Pharmacokinetic Data

If the actual time of sample collection deviates from the nominal time by more than  $\pm 10\%$ , the plasma concentration will be flagged and excluded from the summary statistics.

Individual concentrations deemed to be anomalous will be flagged in the listings and excluded from the summary statistics.

For plasma concentration data the following rules will apply:

- Values that are BLQ will be set to 0 for the calculation of summary statistics.
- If the embedded BLQ value is considered anomalous within the concentration-time profile, this value will be excluded from the summary statistics.
- Where there is NR, these will be set to missing.
- If there are less than three values in the data series, only the min, max and N will be presented. The other summary statistics will be denoted as not calculated (NC). BLQ is considered a value.
- If the values are BLQ, then the arithmetic mean, arithmetic SD, median, min and max will be presented as zero, 0 and the geometric mean and geometric coefficient of variation (CV%) will be denoted as NC.
- Arithmetic mean or median values that are BLQ will be presented as 0, and the geometric mean and geometric CV% will be denoted as NC.

For PK parameters the following rule will apply:

- For the calculation of summary statistics of PK parameters, all non-reportable and NC values in a data series will be set to missing.
- AUCinf and AUClast will be set to NC if they were calculated using fewer than three concentrations, and/or three concentrations if the last is Cmax.
- Geometric mean and coefficient of variation will not be calculated for tlast or tmax.

